8.4.9 Adverse Events of Special Interest

The Investigator must report AESIs to the Sponsor as if it were an SAE (ie, within 24 hours of learning of the AESI). Refer to [Section 8.4.7](#) for contact information.

Definition of an AESI and AESIs that will be monitored in the study are provided in [Section 8.4.1](#).

8.4.10 Overdose or Misuse

Any instance of overdose of IP (suspected or confirmed) must be communicated to the Sponsor as if it were an SAE (ie, within 24 hours of learning of overdose or misuse). Refer to [Section 8.4.7](#) for additional information. Any associated AEs or SAEs must also be reported, and their management should be recorded as described in [Section 8.4.7](#).

8.5 Pharmacokinetics

Serum for PK analysis will be collected at the visits specified in [Table 1](#) and analyzed using a validated bioanalytical method.

Samples will be collected, labeled, stored, and shipped as detailed in the laboratory manual. The time of PK sample collection must be recorded.

The timing of sampling may be altered during the course of the study based on newly available data (eg, to obtain data closer to the time of peak plasma concentrations) to ensure appropriate monitoring.

Samples will be used to evaluate the PK of daxdilimab. Samples collected for analyses of daxdilimab serum concentration may also be used to evaluate safety or efficacy aspects related to concerns arising during or after the study.

Genetic analyses will not be performed on these samples.

8.6 Pharmacodynamics

Whole blood will be collected for the assessment of pDC levels by flow cytometry at the visits specified in the SoA ([Table 1](#)). Daxdilimab binds to ILT7 on the surface of pDCs leading to recruitment of macrophages and NK cells, thus inducing apoptosis and reduction in the number of pDCs.

Samples will be analyzed using a validated analytical method in compliance with the Sponsor's standard operating procedures and analytical requirements. Instructions for sample collection, processing, storage, and shipment are provided in the study-site manual.

8.7 Genetics

Genetics will not be evaluated in this study.

8.9 Immunogenicity Assessments

Serum for immunogenicity ADA analysis will be collected at the visits specified in [Table 1](#) and assessed using a validated immunoassay. Additionally, serum samples should also be collected at the final visit from subjects who discontinued IP or were withdrawn from the study. These samples will be tested by the Sponsor or Sponsor's designee.

[figure not shown]
The ADA samples will be collected at the same time as the PK samples and the time of sample collection must be recorded.

Serum samples will be screened for antibodies binding to daxdilimab and the titer of confirmed positive samples will be reported. Other analyses may be performed to further characterize the immunogenicity of daxdilimab.

Antibodies may be further characterized and/or evaluated for their ability to neutralize the activity of daxdilimab. Samples may be stored for a maximum of 25 years (or according to local

regulations) following the last subject's last visit for the study at a facility selected by the Sponsor to enable further analysis of immune responses to daxdilimab.

Samples will be collected, labeled, stored, and shipped as detailed in the study-site manual.

9 STATISTICAL CONSIDERATIONS

9.1 Primary Hypothesis

No formal statistical hypothesis will be evaluated in the SLE OLE study.

9.2 Analysis Sets

Safety analysis set: The safety analysis set is defined as subjects who received any dose of daxdilimab in this OLE study. The safety, PD, immunogenicity, and exploratory efficacy analyses will be based on the safety analysis set.

Pharmacokinetic analysis set: The PK analysis set is defined as subjects who received any dose of daxdilimab in this OLE study and have at least one measurable PK concentration post dose. The PK analyses will be based on PK analysis set.

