3 OBJECTIVES AND ENDPOINTS

The objectives and endpoints to be evaluated in this study are provided in Table 2.

Table 2 Primary, Secondary, and Exploratory Objectives

Objectives	Endpoints
Primary Objective	
To evaluate the long-term safety and tolerability of 200 mg Q12W daxdilimab	
Incidence of AEs, SAEs, and AESIs
Secondary Objectives	
To characterize the PK, PD, and immunogenicity of daxdilimab	
Daxdilimab concentrations, change in pDCs, and ADA rate
Exploratory Objectives	

Table 2 Primary, Secondary, and Exploratory Objectives

Objectives	Endpoints

ADA = anti-drug antibodies; AE = adverse event; AESI = AE of special interest;

PD = pharmacodynamic(s); pDC = plasmacytoid dendritic cell; [REDACTED];
PK, pharmacokinetic(s); Q12W = every 12 weeks; RECAST SLE = Phase 2 Randomized, Double-Blind,
Placebo-Controlled Efficacy and Safety Study of daxdilimab for the Treatment of Moderate to Severely
Active Systemic Lupus Erythematosus; [REDACTED]
[REDACTED] SAE = serious AE; SLE = systemic
lupus erythematosus; [REDACTED]

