9.3.3.2 Immunogenicity Analysis

Number and percentage of subjects who develop positive ADA will be summarized descriptively.

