4.4 Analysis Sets

4.4.1 OLE Safety Analysis Set

The OLE safety analysis set is defined as participants who received any dose of daxdilimab in this OLE study. The OLE safety analysis set will be used for the safety and pharmacodynamics (PD) analyses.

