4.4.2 Full Analysis Set

The full analysis set is defined as participants who were randomized and received any dose of IP in study RECAST SLE. Participants will be analyzed according to the treatment to which they were randomized in RECAST SLE study. The exploratory efficacy analyses will be based on the full analysis set.

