4.4.3 Any Daxdilimab Analysis Set

The any daxdilimab analysis set includes all participants who receive at least one dose of daxdilimab in study RECAST SLE or this OLE study. The any daxdilimab analysis set will be used for the adverse events and immunogenicity analyses.

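### The SAP summarises ADA only in everyone ever given daxdilimab, so it yields no ADA rate in the OLE-dosed population that the protocol names for this secondary endpoint

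*Protocol*

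**What the plan says.** **Protocol.** ADA rate belongs to the secondary endpoint row in section 3: "Daxdilimab concentrations, change in pDCs, and ADA rate". Section 9.3.3.2 describes the analysis: "Number and percentage of subjects who develop positive ADA will be summarized descriptively". Section 9.2 fixes the population, first by definition, "The safety analysis set is defined as subjects who received any dose of daxdilimab in this OLE study", and then by use, "The safety, PD, immunogenicity, and exploratory efficacy analyses will be based on the safety analysis set".

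**SAP.** Section 4.4.1 keeps the OLE-dosed set for fewer purposes: "The OLE safety analysis set will be used for the safety and pharmacodynamics (PD) analyses". Immunogenicity moves in 4.4.3: "The any daxdilimab analysis set will be used for the adverse events and immunogenicity analyses". Membership of that set needs one daxdilimab dose in RECAST SLE or in the OLE. Section 4.12 applies it to all ADA status categories in Table 5 and names no other set. Section 4.1.1 places the immunogenicity baseline before the first daxdilimab dose in whichever study that occurred.

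Exploratory efficacy also moves, in 4.4.2: "The exploratory efficacy analyses will be based on the full analysis set". That set is wider still: "The full analysis set is defined as participants who were randomized and received any dose of IP in study RECAST SLE".

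**The concern.** The two documents assign different populations to the same secondary endpoint. Protocol 5.1, inclusion criterion 2, bars anyone who stopped investigational product early in RECAST SLE. The any daxdilimab set therefore contains people who could not have entered the OLE, plus any eligible daxdilimab participants who chose not to.

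The time frame shifts as well. For a participant given daxdilimab in RECAST SLE, post-baseline starts in the parent study; for a former placebo participant it starts at OLE Day 1. Table 5 classifies status over the study without saying which study or studies are meant.

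At stake is whether the report can state the ADA rate among people treated in the extension. If the SAP is followed as visible, it cannot. A reader comparing the report with the protocol would find a different denominator and, for one RECAST arm, a longer observation period.

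**Working it through.** **Step 1. The sets side by side.**

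| Analysis | Protocol 9.2 | SAP | OLE dose required by SAP set? |
|---|---|---|---|
| Adverse events | OLE-dosed | OLE-dosed, and any daxdilimab as a second summary (4.9.1) | Yes for the first, no for the second |
| PD | OLE-dosed | OLE-dosed (4.4.1, 4.11) | Yes |
| PK | OLE-dosed with a measurable post-dose concentration | Same (4.4.4) | Yes |
| ADA | OLE-dosed | Any daxdilimab only (4.4.3, 4.12) | No |
| Exploratory efficacy | OLE-dosed | RECAST full analysis set (4.4.2) | No |

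Adverse events have an OLE-only summary beside the combined one. ADA has only the combined one. SAP 4.12 also plans to look at the impact of ADA on PK, but people who never entered the OLE cannot be in the PK set.

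**Step 2. The observation period.** RECAST treatment runs through Week 48, and the OLE runs to Week 56. Assume that daxdilimab started at RECAST Week 0 and that OLE Day 1 falls on RECAST Week 48. The post-baseline period for a completer is then:
- RECAST daxdilimab: 48 + 56 = 104 weeks
- RECAST placebo: 56 weeks

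Changing the set alone would not alter this, because the baseline rule in SAP 4.1.1 governs it.

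**Step 3. The plan's own figure.** Inputs from Protocol 9.5 and SAP 2.3: 195 randomised, 20% assumed to discontinue.

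195 × (1 − 0.20) = 156, which reproduces the stated number eligible. The remainder is 195 − 156 = 39. The documents give no uptake figure, so 156 is a ceiling on OLE entry under this assumption.

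**Step 4. Size of the ADA denominator.** Let *E* be the number dosed in the OLE and *f* the share of non-entrants who had daxdilimab in RECAST SLE. The documents do not give *f*, so I vary it from 1/3 to 3/4.

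- People with no OLE dose = *f* × (195 − *E*)
- Any daxdilimab set = *E* + *f* × (195 − *E*)

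With *E* = 156:

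| *f* | No OLE dose | Any daxdilimab set | Share |
|---|---|---|---|
| 1/3 | 13 | 169 | 7.7% |
| 1/2 | 19.5 | 175.5 | 11.1% |
| 2/3 | 26 | 182 | 14.3% |
| 3/4 | 29.25 | 185.25 | 15.8% |

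If only 80% of those eligible enter, *E* = 0.80 × 156 = 124.8 and 70.2 do not enter. The share is then 23.4/148.2 = 15.8% at *f* = 1/3 and 52.65/177.45 = 29.7% at *f* = 3/4.

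**Step 5. What this could do to the rate (illustration only).** Assume ADA of 10% in OLE-dosed participants and 0% to 30% in the others, with full uptake and *f* = 1/2:

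- (0.10 × 156 + 0 × 19.5)/175.5 = 8.9%
- (0.10 × 156 + 0.30 × 19.5)/175.5 = 12.2%

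The documents supply none of these ADA rates. This step covers the change of denominator only, not the longer observation period in Step 2.

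**The case against.** The any daxdilimab set is a defensible choice for immunogenicity. A pre-daxdilimab baseline is needed to call ADA treatment-induced, and OLE entrants are a selected group because early RECAST discontinuers are excluded. The secondary objective concerns daxdilimab in general; only the primary objective names 200 mg every 12 weeks. No hypothesis is tested, the analysis is descriptive, and Protocol 9.3.1 leaves details to the SAP.

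Most of this stands as a reason to keep the pooled summary. It does not justify dropping the other one. Protocol 9.2 names the population outright, so it is not a detail left to the SAP.

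A reader might infer more than the documents support:

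- *That ADA arising in RECAST SLE will be reported as an OLE finding.* The SAP does not label it so. Its set name and baseline define an any-exposure analysis openly.
- *That 156 people will roll over.* The documents say about 156 will be eligible.
- *That the SAP nowhere acknowledges the change.* The visible text contains no such note and the revision table is empty, but parts of the SAP are not visible.
- *That the efficacy analysis is wrong.* The exploratory objectives and the content of SAP 4.8 are not visible. They may explain a comparison by randomised arm or include an OLE-only summary.

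**Conclusion.** The mismatch for ADA is real and rests on the text alone, not on any assumed figure. The protocol names OLE-dosed subjects, and the visible SAP produces ADA results only for a wider set, with a baseline that can precede OLE entry.

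On the plan's figures, about 8% to 16% of the ADA denominator would have no OLE dose if every eligible subject enters, and about 16% to 30% if 80% do. Both ranges assume *f* between 1/3 and 3/4. A share of the denominator is not a bias of that size: the shift in the ADA percentage is probably modest, and its direction is unknown.

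For exploratory efficacy, the visible text supports only the statement that the two documents name different sets. This should be corrected before database lock. It does not threaten the primary safety objective, since adverse events keep their OLE-only summary.

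**What to change.** 1. In SAP 4.12, add ADA status and ADA incidence on the OLE safety analysis set, by RECAST arm. Incidence is currently optional there. The split by arm goes beyond the protocol but is needed because prior exposure differs.
2. In that table, separate ADA already positive before the first OLE dose from ADA first positive, or boosted, after it. Without this, changing the set still counts ADA that arose in RECAST SLE as post-baseline.
3. Keep the any daxdilimab summary and label it supportive.
4. In Table 5, state for each summary which study period is covered and which baseline applies, and make SAP 4.1.1 and 4.4 agree.
5. For exploratory efficacy, record the departure from Protocol 9.2 and its reason in the SAP, or amend Protocol 9.2.

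The cost is SAP wording and one further table. No new data are needed: the protocol's schedule already has an ADA sample on OLE Day 1, with assessments done before dosing, and Protocol 8.9 provides titres for confirmed positives. The SAP already plans to set the boosting cutoff before database lock.

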9.3 Statistical Analyses

9.3.1 General Considerations

For continuous data, number of observations, mean, standard deviation, median, minimum, and maximum will be reported. For categorical data, percent and frequency will be reported. Data listings will be sorted by treatment group and subject number. Details of the statistical analysis will be specified in a separate SAP.

9.3.2 Primary Endpoint(s) Analysis

9.3.2.1 Safety Analysis

Adverse events will be coded using the Medical Dictionary for Regulatory Activities by system organ class (SOC) and preferred term (PT). In general, if an AE onset is on or after the first OLE dose date, the AE will be considered as a treatment-emergent AE (TEAE) for OLE. All TEAEs will be summarized overall and by SOC and PT, as well as by severity and by relationship to daxdilimab.

For the summary of TEAEs by severity, each participant will be counted only once within a SOC or a PT by using the AEs with the highest intensity within each category. For the summary of TEAEs by relationship to IP, each participant will be counted only once within a SOC or a PT by using the AEs with the greatest reported relationship within each category. TEAE leading to discontinuation of daxdilimab will be summarized by SOC and PT. Treatment-emergent SAEs and treatment-emergent AESIs will also be summarized.

Clinically significant abnormalities in laboratory parameters, vital signs, ECGs, and physical examinations will be recorded as AEs or SAEs. Laboratory assessments, vital signs, and ECGs, as well as their changes from baseline at each visit will also be summarized descriptively.

9.3.3 Secondary Endpoint(s) Analysis

9.3.3.1 Pharmacokinetics Analysis

The PK analysis will be based on the PK analysis set. Descriptive statistics of the serum daxdilimab concentration will be tabulated by visit.

9.3.3.2 Immunogenicity Analysis

Number and percentage of subjects who develop positive ADA will be summarized descriptively.

9.3.3.3 Pharmacodynamics Analysis

The observed count along with the change and percent change from baseline in pDCs will be summarized descriptively.

9.3.4 Exploratory Endpoint(s)Analyses

The exploratory efficacy analyses will be detailed in the SAP.

9.4 Interim Analysis

An interim analysis will not be performed.

9.5 Sample Size Determination

Sample size determination is based on the number of subjects who have completed the treatment period of Study VIB7734.P2.S1 (RECAST SLE). A total of 195 subjects have been randomized in the RECAST SLE study. Assuming that 20% of subjects will prematurely discontinue treatment, there will be a total of approximately 156 subjects who will be eligible for this long-term safety study.

10 SUPPORTING DOCUMENTATION AND OPERATIONAL CONSIDERATIONS

10.1 Appendix 1: Regulatory, Ethical, and Study Oversight Considerations

10.1.1 Regulatory and Ethical Considerations

- This study will be conducted in accordance with the protocol and with the following:
 - Consensus ethical principles derived from international guidelines including the Declaration of Helsinki and the Council for International Organizations of Medical Sciences international ethical guidelines
 - Applicable International Council for Harmonisation (ICH) Good Clinical Practice (GCP) guidelines
 - Applicable laws and regulations
- The protocol, protocol amendments, informed consent form, Investigator's brochure, and other relevant documents (eg, advertisements) must be submitted to an Institutional IRB/IEC by the Investigator and reviewed and approved by the IRB/IEC before the study is initiated.
- Any amendments to the protocol will require IRB/IEC approval before implementation of changes made to the study design, except for changes necessary to eliminate an immediate hazard to study subjects.
- Protocols and any substantial amendments to the protocol will require health authority approval prior to initiation except for changes necessary to eliminate an immediate hazard to study subjects.
- The Investigator will be responsible for the following, as applicable:
 - Providing written summaries of the status of the study to the IRB/IEC annually or more frequently in accordance with the requirements, policies, and procedures established by the IRB/IEC
 - Notifying the IRB/IEC of SAEs or other significant safety findings as required by IRB/IEC procedures
 - Providing oversight of the conduct of the study at the site and adherence to requirements of 21 CFR, ICH guidelines, the IRB/IEC, European regulation 536/2014 for clinical studies, European Medical Device Regulation 2017/745 for clinical device research, and all other applicable local regulations

10.1.2 Financial Disclosure

Investigators and sub-Investigators will provide the Sponsor with sufficient, accurate financial information as requested to allow the Sponsor to submit complete and accurate financial certification or disclosure statements to the appropriate regulatory authorities. Investigators are responsible for providing information on financial interests during the course of the study and for one year after completion of the study.

10.1.3 Informed Consent Process

The Investigator or the Investigator's representative will explain the nature of the study, including the risks and benefits, to the potential subject (or their legally authorized representative) and answer all questions regarding the study.

Potential subjects must be informed that their participation is voluntary. They (or their legally authorized representatives) will be required to sign a statement of informed consent that meets the requirements of 21 CFR 50, local regulations, ICH guidelines, privacy and data protection requirements, where applicable, and the IRB/IEC or study site.

It is the responsibility of the Investigator (or their designee, where allowed by local requirements) to obtain written informed consent from all study subjects. The Investigator or their designee must provide the Sponsor/designee with a copy of the IRB/IEC-approved informed consent document(s) prior to the start of the study at the site. The informed consent must allow for access to the records for at least 25 years to allow for possible future inspections.

The medical record must include a statement that written informed consent was obtained before the subject was enrolled in the study and the date the written consent was obtained. The authorized person obtaining the informed consent must also sign the ICF.

Subjects must be reconsented to the most current version of the ICF(s) during their participation in the study.

The original, appropriately signed and dated ICF must be retained by the Investigator/study site as part of that subject's record. A copy of the signed ICF must be given to the subject.

The ICF must be fully approved by an IRB or an IEC prior to its use with study subjects.

The Sponsor reserves the right to delay initiation of the study at a site where the informed consent document(s) do not meet the standards of this section, applicable regulations, and/or ICH E6(R2).

The ICF will contain a separate section that addresses the use of leftover samples for future research. The investigator or authorized designee will explain to each subject the objectives of the future research. Subjects will be told that they are free to refuse to participate and may withdraw their consent at any time and for any reason during the storage period. A separate signature will be required to document a subject's agreement to allow any leftover samples to be used for future research. Subjects who decline to participate in this future research will not provide this separate signature.

10.1.4 Data Protection and Privacy

All information generated in this study is considered highly confidential and must not be disclosed to any person or entity not directly involved with the study unless prior written consent is obtained from the Sponsor. The subject must be informed that their medical records may be examined by Clinical Quality Assurance auditors or other authorized personnel appointed by the Sponsor, by appropriate IRB/IEC members, and by inspectors from regulatory authorities.

Subjects will be assigned a unique identifier by the Sponsor. Any subject records or datasets that are transferred to the Sponsor will contain the identifier only; subject names or any information which would make the subject identifiable will not be transferred.

The subject must be informed that their personal study-related data will be used by the Sponsor in accordance with local data protection law. The level of disclosure must also be explained to the subject who will be required to give consent for their data to be used as described in the informed consent.

The contract between Sponsor and study sites specifies responsibilities of the parties related data protection, including handling of data security breaches and respective communication and cooperation of the parties.

Information technology systems used to collect, process, and store study-related data are secured by technical and organizational security measures designed to protect such data against accidental or unlawful loss, alteration, or unauthorized disclosure or access.

10.1.5 Committees Structure

10.1.5.1 Safety Data Monitoring Committee

The external, independent Safety Data Monitoring Committee (SDMC) is responsible for safeguarding the interests of study subjects via review of accumulating safety data and for supporting study integrity and interpretability based on their review of ongoing study conduct. The SDMC will provide the Sponsor with recommendations for actions with respect to study conduct and the management of subjects treated under the study protocol. The SDMC members are independent of the Sponsor and any CRO/organization collaborating with the Sponsor on the study.

The SDMC will not be charged with any formal interim analysis, will not conduct a futility analysis, and will not be asked to consider early study completion for efficacy. For additional details, refer to the SDMC Charter.

